#### Non-hematologic DLTs

- Any Grade  $\geq 3$  non-hematologic toxicity, **probably related to study drug**, EXCEPT for the following related AE's:
  - Grade  $\geq 3$  neurologic deficits considered to be due to the effects of tumor, resection, or expected post-surgical morbidities
  - Seizures of any grade, as this is commonly observed in this patient population
  - Grade  $\geq 3$  thromboembolic event, as this is commonly observed in this patient population
  - Grade 3 nausea, vomiting, or diarrhea that resolves to Grade  $\leq 2$  within 3 days of onset
  - Grade 3 headache, insomnia, or amnesia that resolves to Grade  $\leq 2$  within 14 days of onset
  - Grade 3 fatigue that resolves to  $\leq$ Grade 2 within 21 days of onset

- Grade 3 AST or ALT that resolves to  $\leq$ Grade 2 within 21 days of onset
- Grade  $\geq$ 3 CPK, GGT, ALP, hypomagnesemia, or hypophosphatemia that is felt by the investigator to be clinically insignificant
- Alopecia of any Grade.

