#### **7.4.1.2 13-week Rat Study**

A 13-week study evaluated the potential toxicity and toxicokinetic profile of PLX3397 HCl, when administered orally (gavage) at doses of 0.5, 4 and 20 mg/kg/day to Sprague-Dawley rats for 13 consecutive weeks, with a recovery period of 8 weeks. Systemic exposure to PLX3397 generally increased proportionally as dosage increased over the 0.5 to 20 mg/kg/day range. Exposure to PLX3397 was consistently slightly higher for females than for males (up to 1.8-fold for  $AUC_{last}$ ). There were no test article-related clinical observations or effects on body weights, food consumption, ophthalmic examinations, urinalysis, or macroscopic examinations.

At 20 mg/kg/day, PLX3397 was associated with clinical pathology changes suggestive of anemia (erythron changes) generalized stress (lymphopenia and eosinopenia), dehydration (higher albumin, globulin, and total protein), higher AST and ALT, higher fibrinogen, calcium, and cholesterol in males, and lower potassium in females. Additionally, lower absolute and relative spleen and thymus weights were noted for both sexes. Microscopically, males were observed with minimal to mild accumulation of pigment resembling hemosiderin in the proximal tubules of the kidney which was consistent with the observed anemia, minimal or moderate hepatocellular vacuolation, and mild thymic atrophy. Animals from both sexes were noted with mild to moderate generalized bone marrow depletion and minimal to moderate hemosiderin in the spleen. Following an 8 week recovery period, persistent effects consisted of mild hepatocellular vacuolation in 1 of 6 males and mild hemosiderin deposition in the spleen of 5 of 6 females. Taken together, the observed anemia and bone marrow depletion are suggestive of an adverse effect on the hematopoietic system, which was reversible following an 8-week recovery period. Hepatocellular vacuolation observed in males was associated with higher AST, ALT, and cholesterol values at the primary necropsy, persisted to the end of the recovery period, and was considered adverse. There were no histologic abnormalities noted in the epididymides or testes. The NOAEL was considered to be 4 mg/kg/day. This dosage level corresponded to  $AUC_{last}$  and  $C_{max}$  values of 11440 ng•hr/mL and 1271 ng/mL, respectively.

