QT prolongation). At dose levels of  $\geq 600$  mg/day, transient increases in AST and/or ALT have been observed in approximately half the patients. Among the 92 patients with solid tumors treated to date, the most common AEs of all grades have been fatigue, decreased appetite, nausea, vomiting, anemia, hair color change (depigmentation), and diarrhea. With the exception of vomiting and diarrhea, most of these AEs have been considered possibly or probably treatment-related. In the AML study (PLX108-05; n = 15), the most common AEs to date have been fatigue, febrile neutropenia, decreased appetite, nausea, diarrhea, and vomiting. In all studies, drug-related Grade 3 adverse events have been very uncommon. For more details concerning safety, please consult the Investigator's Brochure.

A number of response biomarkers are being assayed to profile the inhibitory activity of PLX3397 on Fms and Kit activity as a function of dose and exposure. These biomarkers include circulating tumor cell (CTC) and CD14+/CD16+ proinflammatory macrophage cell numbers; serum IL-6, IL-1beta and MMP3 concentrations; and markers of osteoclast activity. Most of the soluble markers are not elevated at Baseline in the oncology patients treated to date, so no decrease with treatment can be anticipated. However, in 5 patients to date, CTC counts were elevated at Baseline. In 3 of those 5 patients, CTC values decreased after treatment with PLX3397.

Reductions in the CD14+/CD16+ cell populations have also been observed in all patients treated to date. Serum CSF-1 levels have increased in all patients after initiation of PLX3397 dosing, as would be anticipated from Fms inhibition, resulting in reduced clearance of the ligand. Importantly, higher plasma PLX3397 concentrations are associated with higher elevations of CSF-1, supporting a concentration-dependent pathway inhibition. Urinary NTX concentrations showed a concentration-dependent decrease from Baseline, consistent with osteoclast inhibition. Clinically relevant increases in adiponectin were also observed, with 2-3 fold increases from Baseline generally observed in patients treated at dose levels of 900 mg/day and higher.

[figure not shown]

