#### Hematologic DLTs

- Grade  $\geq 3$  febrile neutropenia
- Grade 4 neutropenia lasting for  $>7$  days (growth factor support allowed)
- Grade 3 thrombocytopenia (platelets  $\leq 50.0/\mu\text{L}$ ) lasting for  $>7$  days

Grade 3-4 lymphopenia is NOT considered a DLT.

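### Probably drug-related seizures and Grade ≥3 thromboembolic events are exempt from the DLT count at every grade, and anaemia is on neither DLT list, so none of these can affect the 2-of-6 dose decision

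*Combined protocol and SAP*

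**What the plan says.** Section 13.13.2 counts as a non-hematologic DLT any toxicity of Grade 3 or higher that is "probably related to study drug, EXCEPT for the following related AE's", followed by a list. Two entries on it are unconditional: "Seizures of any grade, as this is commonly observed in this patient population", and any Grade ≥3 "thromboembolic event, as this is commonly observed in this patient population". The synopsis carries the same two entries, although its lead-in does not describe the excepted events as related.

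Other exemptions are narrower. One begins "Grade 3 fatigue that resolves to" and ends at 21 days. Another begins "Grade 3 headache, insomnia, or amnesia that resolves to Grade" and ends at 14 days. The gastrointestinal and AST/ALT entries have the same form.

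The hematologic list has three entries: febrile neutropenia, prolonged Grade 4 neutropenia and prolonged Grade 3 thrombocytopenia. It adds that "Grade 3-4 lymphopenia is NOT considered a DLT". Anaemia is not mentioned.

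Four other rules depend on the DLT definition or on relatedness:

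- **Sections 13.13.1 and 13.16:** a dose level is unacceptable at 2 or more DLTs in 6 patients. A patient who misses more than 7 dosing days for a reason other than a DLT is replaced, unless the cohort already has 2 DLTs.
- **Section 13.14.1:** during the 11-week window, dose reduction or interruption is allowed only after a DLT, apart from interruption for persistent Grade 3 vomiting.
- **Section 21.1.1:** a level with no more than 2 DLTs in 6 is acceptable, and escalation then follows.
- **Section 23.1:** an event is rated *probably* related if it follows dosing in time, abates when the drug is stopped, and is not reasonably explained by the patient's clinical state. An event that the clinical state or other therapy could have produced is rated *possibly* related.

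**The concern.** The only reason given for the two exemptions is that the events are common in this population. Section 23.1 already deals with that: an event that the disease could explain is rated *possibly* or *not related* and never reaches the DLT clause. The exemption therefore takes effect mainly on events that the protocol's own definition attributes to the drug.

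The DLT count decides which dose level is acceptable, when a higher level opens (including for patients already on study), and so which dose Phase 2 patients receive. If serious drug-attributed events cannot enter the count, a dose level can be accepted with a clean score that does not describe what happened in the cohort.

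Anaemia raises a related question. Section 7.5 lists it among the most common adverse events in solid-tumour patients: "fatigue, decreased appetite, nausea, vomiting, anemia, hair color change (depigmentation), and diarrhea". In the 13-week rat study, "the observed anemia and bone marrow depletion are suggestive of an adverse effect on the hematopoietic system". The initial dog study also called it adverse. Both animal findings were at least partly reversible. Lymphopenia is excluded by name; anaemia is simply absent, so a reader cannot tell whether the omission was intended.

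**Working it through.** The plan states no DLT rate, target toxicity or operating characteristic for the six-patient rule, so there is no figure to reproduce. The check is of the text first, with a binomial illustration after it.

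**Step 1. What the exemption removes.** A non-hematologic event must be Grade ≥3 and *probably* related to qualify. An event rated *possibly* or *not related* scores zero with or without the exemption. The exemption changes the score only for *probably* related events, that is, those not reasonably explained by clinical state.

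**Step 2. Grade.** Neither entry has an upper limit. A *probably* related Grade 4 seizure or Grade 4 thromboembolic event scores zero. A Grade 5 event also scores zero if it can be rated *probably*; see the objection.

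**Step 3. Anaemia.** It is not on the hematologic list, and the general clause covers only non-hematologic toxicity. No grade of anaemia is a DLT.

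**Step 4. The linked rules.**

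| Rule | Effect on a patient with an exempt, probably related event |
|---|---|
| 13.13.1, replacement | If more than 7 dosing days are missed, the reason is not a DLT, so the patient is replaced and leaves the six |
| 21.1.1, replacement | Replaces non-evaluable patients only for reasons unrelated to study drug, which points the other way |
| 13.14.1, dose changes | Read literally, no reduction or interruption is available in the window, because there was no DLT |
| 13.13.1 and 21.1.1, safety review | Data are reviewed before escalation, but no criterion refers to exempt events |

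**Step 5. Size, on assumed rates.** Let p be the proportion of patients with such an event, with no other DLTs. Two are needed to change a 2-of-6 decision:

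P(2 or more of 6) = 1 − (1−p)^6 − 6p(1−p)^5

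- p = 5%: 1 − 0.735 − 0.232 = 0.033
- p = 10%: 1 − 0.531 − 0.354 = 0.114

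So 3.3–11.4% of cohorts would contain two or more such events and be recorded as 0 of 6. Under the Section 21.1.1 wording three are needed. Subtracting 15p²(1−p)^4 gives 0.2% at p = 5% and 1.6% at p = 10%.

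**Step 6. With other DLTs present.** Take an assumed 10% of patients with a counted DLT and a further 10% whose only severe toxicity is uncounted. The 2-of-6 rule rejects the dose with probability 11.4% as written (p = 10%). It would reject with probability 34.5% if all were counted (p = 20%: 1 − 0.262 − 0.393 = 0.345).

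**The case against.** The best defence is that the gap is narrow in practice. Seizures and clots are expected in glioblastoma, so most will be rated *possibly* related and fail the relatedness test whatever the exemptions say. Section 7.5 reports that drug-related Grade 3 events have been very uncommon, with 107 patients treated, and neither event type is among the common ones listed. Safety data are reviewed before every escalation, the Medical Monitor reviews serious events, and the sponsor may stop the study at any time. The exemptions carry a stated reason, and the synopsis and Section 13.13.2 agree on them.

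Much of this stands. The number of affected events may be small, and the reviews are a real safeguard. But if nearly all background events already fail the relatedness test, the exemption is not needed to keep them out. What it removes is the remainder, which the protocol attributes to the drug. The reviews also have no rule for these events, and Section 21.1.1 says that escalation follows from an acceptable count.

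Four stronger readings are tempting, and the documents do not support them:

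- **That 26–47% of cohorts are affected.** That is the chance of at least one event at the assumed rates (1 − 0.95^6 to 1 − 0.90^6). One event alone does not change a 2-of-6 decision.
- **That drug-related deaths plainly score zero.** *Probably* includes abatement on stopping the drug. If all the listed features are required, a fatal event cannot be rated *probably* at all. Grade 4 is the clear case.
- **That every other exemption is capped at Grade 3.** Neurologic deficits, certain laboratory changes and alopecia also have no cap. The first is limited by cause and the second by clinical insignificance; alopecia is not a comparable hazard.
- **That life-threatening anaemia has been seen.** Section 7.5 lists anaemia among events of all grades and reports no Grade 4 case.

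**Conclusion.** The point holds as a mismatch between the DLT exemptions and the protocol's own definition of relatedness. *Probably* related Grade 4 seizures and thromboembolic events score zero in the rule that supports the RP2D, and so would Grade 5 events if they can be given that rating. The replacement rule in Section 13.13.1 can also take these patients out of the six. The status of anaemia is unstated.

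The size cannot be taken from the documents. The 3.3–11.4% figure assumes that 5–10% of patients are affected, that patients are independent, that there are no other DLTs, and that the 2-or-more rule applies. Lower event rates, or the Section 21.1.1 wording, make it smaller; counted DLTs in the same cohort increase the effect on the decision. The documents do not show that any cohort was misjudged, or which grades ought to count.

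**What to change.** Amend the protocol to reconcile the DLT lists (synopsis and Section 13.13.2) with Sections 13.13.1, 13.14.1, 21.1.1 and 23.1, so that it states:

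1. whether *probably* related Grade 4–5 events of the exempt types count towards the dose-level decision, with a reason if they do not;
2. whether severe anaemia counts;
3. how a fatal event is rated, given the abatement feature in Section 23.1;
4. whether a patient with such an event may be replaced, and whether the limit on dose changes in the window applies to that patient.

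The clinical thresholds are for the sponsor and investigators to set. The same amendment should settle whether 2 DLTs in 6 is acceptable, since Sections 13.13.1 and 13.16 disagree with Section 21.1.1.

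Whatever is decided, tabulate exempt Grade ≥3 events and severe anaemia by cohort and relatedness, including replaced patients, beside the DLT counts that support escalation and the RP2D. If Phase 1b is already complete, that table is the part still worth doing.

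The cost is a few sentences and one table. The downside is that an occasional background event rated *probably* related may weigh on a dose decision.

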### 13.13.3 Liver Enzyme Abnormalities

PLX3397 can cause abnormalities in liver function that in some cases have been considered severe. Taking PLX3397 together with other medications that can cause liver function abnormalities may further increase the risk of severe liver injury. Liver laboratory abnormalities should be managed with dose reduction, treatment interruption, or treatment discontinuation.

Discontinuation of treatment should be considered if any of the following occurs:

- ALT or AST  $>8$  x ULN
- ALT or AST  $>5$  x ULN for more than 2 weeks
- ALT or AST  $>3$  x ULN and Total bilirubin (Tbili)  $>2$  x ULN or INR  $>1.5$
- ALT or AST  $>3$  x ULN with the appearance of fatigue, nausea, vomiting, right upper quadrant pain or tenderness, fever, rash, and/or eosinophilia ( $>5\%$ )

Plexxikon should be informed as soon as possible when any of the above occurs.

In the event that study medication is discontinued for any of the reasons above, and if enzyme elevations persist for more than 2 weeks and no clear alternative cause of the abnormalities are found, consideration should be given towards obtaining a liver biopsy, if there are no contraindications (e.g., bleeding diathesis).

Generally, rechallenge of patients with significant AST/ALT elevations ( $>5$  x ULN, Grade 3) should not be attempted. Rechallenge can be considered if the patient has shown important benefit from the drug and other options are not available but must be discussed with the medical monitor prior to re-starting. The patient should be made aware of the potential risk, and consent to the rechallenge, and the institutional review board consulted.

If there is Grade 2 or higher ALT or AST elevation (i.e.  $>3$ x upper limit of normal) at any time during treatment, the patient should be followed closely, which includes the following:

- Repeating liver enzyme and serum bilirubin tests two or three times weekly. Frequency of retesting can decrease to once a week or less if abnormalities stabilize or the trial drug has been discontinued and the patient is asymptomatic.
- Obtaining a more detailed history of symptoms and prior or concurrent diseases.

- Obtaining a history of concomitant drug use (including nonprescription medications and herbal and dietary supplement preparations), alcohol use, recreational drug use, and special diets.
- Ruling out acute viral hepatitis types A, B, C, D, and E; autoimmune or alcoholic hepatitis; NASH; hypoxic/ischemic hepatopathy; and biliary tract disease.
- Obtaining a history of exposure to environmental chemical agents.
- Obtaining additional tests to evaluate liver function, as appropriate (e.g., INR, direct bilirubin).
- Considering gastroenterology or hepatology consultations.

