**Table 4: Dose Modification Guidelines for Liver Function Abnormalities**

Toxicity Grade CTCAE v4.0	Initial Action	Outcome	Action
ALT or AST Grade 2 (>3-5 × ULN); No increase in bilirubin a	Re-check ALT and AST immediately Hold study drug Monitor weekly b Check for changes to medications and for symptoms	Resolution to Grade 0–1 or baseline (no bilirubin increase)	Restart on resolution Grade 0–1 or baseline at 1 dose lower (reduce by one 200 mg capsule)
Grade 3 ALT or AST increase (>5-20 × ULN); No increase in bilirubin a	Re-check ALT and AST immediately Hold study drug Monitor 2x/week b Check for changes to medications and for symptoms	Resolution to Grade 0–1 or baseline (no bilirubin increase) within 14 days	Restart on resolution to Grade 0–1 or baseline at 1 dose lower (reduce by one 200 mg capsule)
		ALT and AST not decreasing within 14 days of holding study drug	Proceed to liver evaluation as outlined in Table 5 . Restart only on resolution to Grade 0-1/baseline at 1 dose lower (reduce by one 200 mg capsule); For max AST or ALT >8 × ULN, consult with medical monitor prior to re-start
Grade 4 ALT or AST (>20 × ULN)	Discontinue treatment Monitor 2x/week until resolution to Grade 2 Follow-up until resolution Grade 0–1 or baseline Check for changes to medications and for symptoms	All outcomes	Discontinue treatment; Proceed to liver evaluation as outlined in Table 5 . If clear confirmed alternate cause, restart on resolution to Grade 0–1 or baseline at 1 dose lower (reduce by one 200 mg capsule)
Any grade ALT or AST increase a with any bilirubin increase or signs of hypersensitivity	Discontinue treatment Monitor 2x/week until resolution to Grade 2 Follow-up until resolution Grade 0-1 or baseline Check for changes to medications and for symptoms	All outcomes	Discontinue treatment; Proceed to liver evaluation as outlined in Table 5 . If clear confirmed alternate cause, restart on resolution to Grade 0–1 or baseline at 1 dose lower (reduce by one 200 mg capsule)

ALT = alanine aminotransferase; AST = aspartate aminotransferase;

CTCAE = Common Terminology Criteria for Adverse Events; ULN = upper limit of normal

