a An increase in bilirubin is defined as all of the following: total bilirubin >ULN, total bilirubin >20% above baseline, and direct bilirubin is >ULN. If all of these conditions are met, then bilirubin is considered increased and should be immediately re-checked. Pexidartinib treatment should be immediately discontinued for increased bilirubin unless and until there is a clear, confirmed alternate cause.

b If ALT, AST, or bilirubin worsens during the monitoring period, follow the applicable guidance for the worst toxicity grade.

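### After a Grade 3 ALT/AST rise without bilirubin increase, 13.13.3 and Table 4 give different re-exposure rules with no stated precedence, and 13.14.1 read literally blocks liver holds in the Phase 1b DLT window

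*Combined protocol and SAP*

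**What the plan says.** Section 13.13.3 makes re-exposure the exception: "Generally, rechallenge of patients with significant AST/ALT elevations ( $>5$ x ULN, Grade 3) should not be attempted". It leaves a narrow route: "Rechallenge can be considered if the patient has shown important benefit from the drug and other options are not available". Such a case "must be discussed with the medical monitor prior to re-starting", and further: "The patient should be made aware of the potential risk, and consent to the rechallenge, and the institutional review board consulted".

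Table 4 covers Grade 3 ALT or AST (>5 to 20 x ULN) with no bilirubin increase. The drug is held. If the rise resolves within 14 days, the action is: "Restart on resolution to Grade 0–1 or baseline at 1 dose lower (reduce by one 200 mg capsule". If enzymes are not falling within 14 days, the Table 5 evaluation comes first, then: "Restart only on resolution to Grade 0-1/baseline at 1 dose lower (reduce by one 200 mg capsule". That row names the medical monitor for peaks above 8 x ULN. More broadly, 13.14.2 wants every adjustment made with the Medical Monitor, and Table 5 says the same of restarts.

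For Phase 1, 13.14.1 cites only Table 3, whose title excludes liver function. In the 11-week DLT window it permits reductions and interruptions only if the patient has a DLT; the one further allowance is interruption for persistent Grade 3 vomiting. Section 13.13.2 exempts Grade 3 AST or ALT from the DLT definition if it falls to Grade 2 or lower within 21 days.

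The retest schedules at Grade 2 also differ. Section 13.13.3 asks for: "Repeating liver enzyme and serum bilirubin tests two or three times weekly". Table 4 has an immediate re-check, then weekly monitoring, with footnote b: "If ALT, AST, or bilirubin worsens during the monitoring period, follow the applicable guidance for the worst toxicity grade".

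**The concern.** A site whose patient has recovered from a Grade 3 transaminase rise finds two defaults. One says do not re-expose except under several safeguards; the other says resume at a lower dose. Whether the patient is asked for specific consent, and whether the IRB hears of it, depends on which page the site reads. In the Phase 1b window the site meets a further obstacle: 13.13.3 wants liver abnormalities managed by reduction, interruption or discontinuation, yet 13.14.1 appears to withhold the first two until the rise counts as a DLT.

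Patient safety is at stake. Section 13.13.3 acknowledges that liver abnormalities on PLX3397 have in some cases been severe and that co-medication may add to the risk. Every patient also receives temozolomide, and Attachment 4 includes a letter reporting hepatic injury, including fatal hepatic failure.

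**Working it through.** The plan has no figure to reproduce here. The check is a comparison of texts and a count.

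**1. Conditions for re-exposure after >5 x ULN, bilirubin not increased.**

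| Condition in 13.13.3 | In Table 4, Table 5 or 13.14.2? |
|---|---|
| Important benefit | No |
| No other options | No |
| Medical monitor discussion | Yes (13.14.2 and Table 5 generally; Table 4 for peaks >8 x ULN) |
| Patient informed and consenting | No |
| IRB consulted | No |

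Five conditions, one shared: 5 - 1 = 4 absent. Table 4 has a precondition of its own, resolution to Grade 0-1 or baseline.

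**2. Do the texts cover the same patient?** Take a hypothetical asymptomatic rise to 6 x ULN, bilirubin and INR normal, resolving in ten days. It meets none of the 13.13.3 triggers for considering discontinuation: it is not above 8 x ULN, not above 5 x ULN for more than two weeks, and has no bilirubin, INR or symptom component. It still falls under the 13.13.3 rechallenge sentence, which is keyed to >5 x ULN. Table 4 restarts this patient one capsule lower.

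**3. Which text governs?** Section 13.14.2 says that Phase 2 dose changes follow the guideline tables. It first cites Tables 3.1 to 3.3, which is clerical; later in the same section it names Tables 3, 4 and 5. Section 13.13.3 sits under 13.13, whose heading refers to the Phase 1b portion. But the body of 13.13.3 names no phase and covers rises at any time during treatment, Table 4's title names no phase, and 13.14.1 (Phase 1) borrows Table 3 from under the Phase 2 heading. No sentence ranks the two texts or cross-refers them.

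**4. The DLT window.** Apply 13.14.1 literally to the patient in step 2. The rise resolves in 10 days, which is within 21, so it is not a DLT and no interruption is permitted. Now take a rise staying above 5 x ULN for 15 to 21 days before falling to Grade 2. Section 13.13.3 asks for discontinuation to be considered once two weeks have passed. The DLT exemption runs to day 21. For 21 - 14 = 7 days, discontinuation is on the table under one section while a hold is still not permitted under the other.

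**5. Retesting.** For a new Grade 2 rise the starting frequency is two or three times weekly in 13.13.3 and weekly in Table 4. The gap is small: Table 4 adds an immediate re-check and escalation on worsening, and 13.13.3 lets the frequency drop once values stabilise.

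**The case against.** The strongest reply is that the texts can be reconciled. Rechallenge could mean re-exposure after discontinuation and restart could mean resumption after a hold: the rechallenge paragraph follows the discontinuation and biopsy paragraphs, 13.13.3 itself lists interruption and reduction as options, and section 7.5 foresees Grade 3 rises handled by a drug holiday and possible dose reduction. This does not hold, because the rechallenge rule is keyed to >5 x ULN, not to discontinuation, and 13.13.3 itself speaks of re-starting.

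The second reply is that the rules belong to different phases. This stands in part. A reader might infer that the plan gives no indication of phase at all; that goes too far, since 13.14.2 assigns the tables to Phase 2 and a heading places 13.13.3 under Phase 1b. What is missing is any statement of how far 13.13.3 reaches, and any reason why consent and IRB steps would apply in one phase only.

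The third is that both texts are advisory. True: 13.13.3 says generally, and 13.14.2 calls its parameters a guide that does not override clinical judgment. In 13.13.3 only the monitor discussion is worded as mandatory, and that step is in both routes. Table 4 is also the stricter text on initial holds (every Grade 2 or 3 rise) and on bilirubin. So it would be wrong to infer that Table 4 is lax overall or that its restart is automatic. Even so, advisory texts with opposite defaults do not tell a site whether consent is expected.

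On the DLT window, 13.13.1 contemplates missed drug for reasons other than a DLT, so the literal reading is not the only one, and 13.15 always allows discontinuation. The conflict with 13.13.3's call for interruption remains on the page.

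**Conclusion.** The inconsistency is real and bears on patient safety. After Grade 3 ALT/AST without bilirubin increase, 13.13.3 advises against re-exposure outside a five-condition exception, and Table 4 provides a lower-dose restart on resolution with one of those five conditions. Precedence is unstated. In Phase 1b, 13.14.1 read literally does not permit the liver hold that 13.13.3 calls for until the rise counts as a DLT.

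The number of patients affected cannot be derived. Section 7.5 describes typical rises of about 1.5 x ULN, very uncommon drug-related Grade 3 events, and some Grade 3 elevations; it gives no rate above 5 x ULN, so few patients may be affected. A reader might size the problem as the share of enrolled patients in Phase 2. That is not supported: it counts patients who never have a Grade 3 rise, it assumes the strict phase split under which the rules do not collide, and the Phase 2 total of 44 in section 21.2 already includes 7 Phase 1 patients (37 + 7). Nor do the documents show which re-exposure default is the right one. The primary endpoint, sample size and test are unaffected.

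The DLT-window conclusion assumes that the DLT-only limit in 13.14.1 means what it says.

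**What to change.** 1. In 13.14.1, cite Tables 4 and 5, and except liver-related holds and reductions from the DLT-only limit. Adding the citation without the exception would create a new conflict.
2. State that one liver rule set covers both phases. Keep Table 4's hold and bilirubin rules. Cross-refer 13.13.3 and Table 4, with a stated precedence for re-exposure after >5 x ULN, and require medical monitor agreement and documented patient consent before any such restart.
3. Leave the benefit, no-other-options and IRB conditions to the sponsor's safety group. Making important benefit mandatory is a trade-off: the baseline scan for progression comes about 3-4 weeks after RT (synopsis), so benefit would be hard to show in Cycles 1 and 2, and early reversible rises could in practice become permanent discontinuations.
4. Use one initial retest frequency at Grade 2.

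The cost is amendment wording and site retraining; the laboratory tests are already specified. Some restarts will be delayed. In Phase 1b, a patient who misses more than 7 days of PLX3397 in Cycles 1 and 2 without a DLT is replaced (13.13.1), so permitting liver holds may mean a few replacement patients.
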